- e. *Audio recordings of CM sessions*. CM staff in both implementation conditions will be required to submit audio recordings of CM sessions once per month in order to receive performance feedback and P4P incentives. Submissions will be made using the Brown CIS recommended solution of Virtru encrypted email. A Brown research staff member will email each site a reminder that audio recordings are due using Virtru encrypted email: as long as providers reply to this email, audio recordings will be encrypted. Use of Virtru will be demonstrated during both the upfront didactic training and the ongoing monthly coaching calls.

9. Key Measures.

- a. *Implementation outcomes*. Our **Primary Aim** tests the effectiveness of the two implementation conditions (ATTC vs. E-ATTC) on CM Exposure, CM Competence, and CM Sustainment.
 - i. **CM Exposure**. This is a patient-level measure of the number of CM sessions delivered per patient during the 9-month Implementation phase. As described above, at each site, data will be extracted from the medical record (by center staff blind to condition) and entered into the Medical Record Data Extraction Form for the 25 patients enrolled in the study (25 patients * 30 sites = 750 patients) at the end of the Implementation phase. A Medical Record Data Extraction form will be filled out for every Self-Report Data Form completed in the patient medical record. Based on empirically derived benchmarks from prior RCTs,¹⁰ 10 or more complete CM sessions per patient (out of a maximum of 24) is the target level of CM Exposure to merit P4P incentives. To reach the target level of CM Exposure for a given patient, at least 10 Medical Record Data Extraction forms must be completed.
 - ii. **CM Competence**. This is a staff-level measure of staff's skill in CM delivery during the 9-month Implementation phase. Each month, CM staff will submit audio-recordings, one of which will be randomly selected for rating by coders blind to implementation condition using the CM Competence Scale¹² (CMCS). The scale contains 9 items scored from 1 to 7, with 7 denoting excellent competence. Based on empirically derived benchmarks from prior RCT research,¹³ an average CMCS score of 5.8 across items is the target to earn P4P incentives. A continuous measure of CMCS scores will be created for each staff on a monthly basis.
 - iii. **CM Sustainment**. This is a patient-level measure of the number of CM sessions delivered per patient during the 12-month Sustainment phase. Using the same protocol as for CM Exposure, data will be extracted at the end of the Sustainment phase from 25 randomly selected patients meeting eligibility criteria (i.e., newly admitted to OUD pharmacotherapy during the Sustainment phase; 25 patients * 30 sites = 750 patients). A continuous measure of the number of sessions received, as counted by the number of Medical Record Data Extraction forms completed, will be created for each patient.

b. *Patient outcomes.* Our **Secondary Aim** tests the effectiveness of the two implementation conditions (ATTC vs. E-ATTC) on two patient outcomes: Opioid Abstinence and Opioid-Related Problems.

- i. **Opioid Abstinence.** Patient abstinence from opioids will be assessed via 3- and 6-month post-baseline interviews, during which patients will self-report days of abstinence using the Timeline Followback (TLFB).²⁰ Abstinence will be corroborated via dip urine screens from Redwood Toxicology testing for: heroin/opiates, oxycontin, benzodiazepines, cocaine, methamphetamines, and THC. In addition, at the request of participating centers, single-panel screens will test for fentanyl, a highly lethal opioid not detected in multi-panel screens. A urine screen negative for all opioids (heroin/opiates, oxycontin, fentanyl) will be required for coding of 90 days abstinence. Other drug use detected via the TLFB or urine will be examined as covariates in the analysis.
- ii. **Opioid-Related Problems.** Opioid-related problems will be assessed via patient self-report at 3- and 6-months post-baseline using the Substance Problem Index,²¹ which is a count of DSM symptoms experienced by the patient (range from 0 to 11). Both Drs. [name] and [name] have successfully used this index²²⁻²⁴ in prior studies. The index will be tailored to focus specifically on problems due to opioids.

c. *Putative mediators.* Our **Exploratory Aim** tests putative mediators of implementation outcomes: implementation climate and leadership engagement. Organization-level scoring is described in **Analytic Plan**. The putative mediator scales are measured at the start of the Preparation phase and the midpoint of the Implementation phase.

- i. **Implementation climate.** A 6-item measure of CM staff and leadership shared perceptions regarding the extent to which the innovation being implemented (i.e., CM) is expected, supported, and rewarded within their center.²⁵ Each item is scored on a 5-point Likert scale. This well-validated, brief measure was developed by Jacobs and colleagues, and following published guidelines, we calculate a scale mean for each staff member.
- ii. **Leadership engagement.** A 4-item measure of CM staff and leadership shared perceptions regarding the extent to which leadership is committed to, involved in, engaged in, and accountable for the implementation of the innovation (i.e., CM). Each item is scored on a 5-point Likert scale. Developed and validated as part of [name] current NIDA-funded project, this measure has demonstrated excellent internal reliability ($\alpha = .94$) and has been shown to be a significant predictor of staff-level implementation fidelity ($\beta = .18, p < .05$).²⁶

d. *Covariates.* We measure potential baseline covariates at the patient, staff, and organization level. These measures are only administered at baseline. Specific measures used include:

- i. **Baseline organization form.** A form measuring baseline characteristics including years of operation, number of patients served, and medications prescribed.
- ii. **Implementation Readiness.** A well-validated 12-item pragmatic measure developed by Shea and colleagues²⁷ will assess readiness to implement CM.
- iii. **CM Attitudes.** A brief measure of attitudes towards CM, as well as providers' perception of its effectiveness and acceptability will be administered. This measure was developed by the NIDA Clinical Trials Network and has been used in multiple NIDA funded studies.
- iv. **Provider demographics.** At the provider-level, we measure staff tenure, education level, and attitudes towards CM.

- v. Patient demographics. At the patient-level, we measure biological sex, race/ethnicity, age, and problem severity.
- vi. Patient clinical characteristics. At baseline, we administer a general measure of global health functioning. This scale was developed by the NIH funded patient-reported outcomes study and is used in multiple NIH funded studies.
- e. *Other Measures*. As noted in prior sections, we also collect some additional measures.
 - i. *Patient contact information*. At the baseline assessment, we collect multiple forms of patient contact information, which will be stored separately from other study data. We gather this information from patients either over the phone or via face-to-face sessions and store it on paper forms kept in locked filing cabinets separate from other study measures.
 - ii. *Patient locator forms*. At the baseline assessment, patients complete locator forms and sign locator letters with contact information of 2-3 close family members or friends in order to enable us to retain participants for the follow-up assessments. These data will be stored separately from other study data. We gather this information from patients from patients either over the phone or via face-to-face sessions and store it on paper forms kept in locked filing cabinets separate from other study measures.
 - iii. *Provider CM knowledge*. Immediately following the full day training, providers will complete a measure of CM knowledge to ensure that they have sufficient understanding of CM principles to proceed to role plays. Providers that do not score at least 16 out of 20 will receive additional customized support from the ATTC trainer.

10. Analytic Plan.

- a. All analyses will be conducted following intent-to-treat principles.^{28,29} Missing data will be multiply imputed following recommendations of the National Research Council.³⁰ We will test the appropriateness of assumptions underlying the use of multiple imputation using sensitivity analyses.³¹
- b. For the **Primary and Secondary Aims**, we test a series of multilevel models in which patients (Level 1) are embed within staff (Level 2) and within centers (Level 3). Consistent with Raudenbush and Bryk's multilevel modeling approach,³² the proportion of variance to-be-explained at each level will be examined as an initial step. Next, following a decomposed-first strategy that advocates for starting with moderation-focused hypotheses to avoid biases associated with conflated effects,³³ we conduct multilevel regressions testing the extent to which our covariates significantly moderate the hypothesized relationship between condition and outcome. We test covariates at three levels: organizational (e.g., years of operation, number of patients, medications prescribed, implementation readiness), staff (e.g., tenure, education, CM attitudes), and patient (e.g., age, race, biological sex, problem severity). If moderation is not found, covariates will be controlled for as predictors. Condition assignment (ATTC vs. E-ATTC) will be the primary independent measure of interest for analyses. In addition to reporting statistical significance, we will report the effect size (ES) using Cohen's d .³⁴
- c. For the **Exploratory Aim**, we again test a series of 3-level models. For each mediator, the average correlation within group (r_{wg}) will be computed to determine whether aggregation of staff level responses to the organizational-level is warranted. Values of r_{wg} range from -1.00 to 1.00, with values $\geq .60$ representing acceptable agreement.³⁵ Centers with r_{wg} values $< .60$ will be excluded from analysis. Exploratory analyses will apply a Baron and Kenny³⁶ style mediation approach,

which uses centering within context and includes a group mean at level-3 (CWC[M]).³⁷ Procedurally, first the outcome will be regressed on the condition variable (ATTC vs. E-ATTC) in a multi-level regression. Next, the outcome will be predicted by both condition and the group mean centered mediator (e.g., implementation climate) in a multi-level regression. Third, the mediational effect will be calculated by subtracting the estimated coefficient associated with condition in step two from the estimated coefficient associated with condition in step one. This method will allow the between-group mediation effect to be partitioned from the within-group mediation effect, which is important since between-group mediation is the effect of interest. Although significance of the mediation effect will be calculated using the Freedman and Schatzkin³⁸ *t* statistic, we also will report ES, which are not influenced by power.

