1. **Study Purpose.** The primary purpose of this study is to experimentally evaluate two different comprehensive training models to train opioid treatment centers in an evidence-based behavioral treatment called contingency management (CM), which is the provision of motivational incentives for reaching specific treatment benchmarks. An exploratory goal of this study is to test whether theorized mechanisms of change – implementation climate and leadership engagement – mediate the effect of implementation condition on outcomes. Conduct of this study will address critical public health needs by (a) informing how CM, an evidence-based practice, should be implemented in OUD treatment centers, (b) improving the outcomes of OUD patients receiving treatment in the community, and (c) advancing knowledge about why and how implementation strategies work.
2. **Overview of Study Design.** A Type 3 Hybrid Trial will be conducted collecting data on both implementation and patient outcomes. We will use a 3-cohort staggered cluster RCT design. The unit of randomization will be opioid treatment centers. Centers will receive one of two comprehensive training conditions: the standard training provided by the New England Addiction Technology Transfer Center (ATTC training) or an enhanced condition that also provides leadership coaching and provider incentives (E-ATTC training). The primary research activities will be measuring the effectiveness of the training initiatives by gathering data from organizations, providers and patients.

Every 12-16 months, 10 OUD centers will be randomly selected to initiate study activities (10 centers X 3 cohorts = 30 centers). Prior to randomization, each center will complete a Baseline Organizational Assessment (described further in the Measures section) to collect organizational background data (e.g., years in operation, number of patients served annually, number of staff, medications prescribed, implementation readiness). Using these data, urn randomization procedures (balancing on number of patients served and percent of patients receiving methadone) will be used to randomize centers to either the ATTC or the E-ATTC condition. Centers in both conditions will complete a 5-month Preparation phase, a 9-month Implementation phase, and a 12-month Sustainment phase (26 months total). In both conditions, providers will record their delivery of CM in the electronic medical record and will audio record one CM session per month.

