Because this is an implementation trial, the goal is to help opioid treatment centers in both conditions to integrate CM into their routine clinical care. CM is a well-established, evidence-based behavioral intervention for the treatment of opioid use disorder; in fact, it has the strongest evidence base of any behavioral intervention. Its effectiveness as an

adjunct to medication has been documented in multiple systematic reviews and meta-analyses, it has large to very large effects, and in head to head comparisons, it has outperformed other behavioral interventions. Opioid treatment centers that participate in this study will receive training designed to help them universally offer CM to **all** newly admitted patients. In addition, front desk staff at the opioid treatment centers will be asked to give consent to contact forms to all newly admitted patients. Research staff will then make contact with interested patients and will obtain informed consent from up to 25 CM patients at each organization (25 patients * 30 organizations = 750 patients). Patients that provide informed consent will complete follow-up assessments at 3-months and 6-months post intake, to help assess whether the organizational training had positive effects on patient outcomes. Patients that do not wish to enroll in the study will still be eligible to receive CM sessions. In addition, those patients that do not wish to receive CM sessions can decline to receive CM or opt out of CM prize draws at any time. All patients will receive the standard of care at the opioid treatment center, which may or may not include CM.

3. **Study Participants.** Our primary unit of recruitment is OUD treatment centers. Within each center, we recruit a small number of providers to complete measures of organizational climate and functioning, to submit audio recordings of their sessions, to receive performance feedback on their sessions, and (for those randomized to E-ATTC) to receive performance incentives. We also consent 25 patients per center to complete study assessments so that we can track if our organizational intervention has a positive effect on patient outcomes.

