one of three trained CM staff will turnover during the project's first two phases, each center will be required to identify one or more replacement CM staff. Thus, if one of the initially trained CM staff withdraws from the study for any reason during the Preparation or Implementation phase, a replacement CM staff will be immediately trained.

- c. *Community-based OUD treatment center patients (Patients).* Each center will agree to deliver CM to all patients newly admitted over a 6-month period. In addition, each center will be asked to enroll approximately one eligible CM patient per week to complete research assessment measures. Eligible patients will be: a) adult patients, b) newly admitted to the opioid treatment center within the past 30 days, and c) prescribed any FDA-approved OUD medication. To optimize ecological validity, exclusion criteria will be minimal and will only include issues that could interfere with the ability to complete a brief intake interview including acute intoxication, acute psychosis, acute mania, or cognitive impairment (prohibiting comprehension of the consent process), as reported by opioid treatment center staff or observed by research staff. We focus on newly admitted patients as opposed to those established in treatment because the need is highest among these patients: drop-out rates and missed doses are higher during the first 6 months of treatment (i.e., the "induction phase") than any subsequent period.

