- c. *Patients.* Front-desk receptionist staff in each of the participating centers will give new patients that present to treatment a consent to contact form. Patients that are interested in participating and sign a consent to contact form will then receive a call from the local research team to set up a time to complete the consent and baseline assessment process. It is expected that opioid treatment centers will only refer eligible patients. But as a safeguard, at the start of the call, research staff will confirm eligibility for the study using the brief 3-item **Patient Screener**. To reduce the amount of PHI stored at each treatment center, consent forms will be administered to eligible patients electronically and will use electronic signatures. Patients will have the option of completing the consent process via phone at a location of their choosing if they have access to the internet and can review the consent form during the phone call, via phone in a private room at the opioid treatment center with a study research tablet that contains the consent form, or in person with research staff at the opioid treatment center. Patients will receive a copy of the form electronically or via mail: their preference will be assessed in the consent form. Estimates from the 30 participating centers indicate the average patient flow is 17 new patients per month or 102 patients per 6-month period. Our recruitment targets conservatively estimate that 25% of new patients will be enrolled, for a total of 750 patients (30 clinics x 25 clients per center). If necessary to reach our target sample size (750), we will oversample from larger centers; if so, we will monitor patient enrollment and ensure a balanced number of patients are assigned to the two implementation conditions (ATT vs. E-ATT).

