 - b. *Implementation.* During this 9-month phase, trained CM providers in both conditions begin implementing the CM protocol with patients. Additionally, in both conditions, CM providers will submit an audio recording of at least 1 CM session per month and will receive ongoing performance feedback on their CM competence from an ATTC trainer. More specifically, each month one CM session recording per CM will be submitted for review using Virtru encrypted email. Once received, a research staff member will rate the session using the 9-item **CM Competence Scale** (CMCS) for Reinforcing Compliance.¹² Once the rating has been done, CM providers will be emailed feedback reports. Staff will also participate in condition-specific monthly group coaching calls. Centers randomized to E-ATTC will receive two additional elements of support: (1) ELC and (2) P4P incentives. Throughout Implementation, as part of ELC, each center leadership will participate in monthly center-specific coaching calls. As part of P4P, CM providers will receive monetary bonuses for achieving two pre-defined goals based on benchmarks in RCT research with OUD counselors: (a) CM Exposure¹³ (i.e., meeting a target number of 10 sessions per patient) and (b) CM Competence¹⁰ (i.e., meeting a target score of 5.8 on the CMCS). The provider incentive structure is described more in depth in Section 7b. One month before the end of the Implementation phase, the ELC will return for an in-person sustainment-centered planning meeting.

c. **Sustainment.** No ATTC or E-ATTC activities will be provided during this 12-month phase, though sustainment of activities will be actively measured.

7. Implementation Conditions: ATTC vs. E-ATTC.

a. **ATTC.** Participating staff from all centers will receive the ATTC strategy, under [name] oversight.

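### CM Exposure is counted only in consented patients recruited after center randomization, probably the same patients on whom E-ATTC bonuses are paid, so it is weak evidence of delivery to all new admissions

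*Combined protocol and SAP*

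**What the plan says.** The protocol and SAP are one document; the references are to the numbered items of its Detailed Study Methodology.

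- **Randomization (item 2).** "The unit of randomization will be opioid treatment centers". The organizational form comes first: "Prior to randomization, each center will complete a Baseline Organizational Assessment". A 5-month Preparation phase follows, and only in the 9-month Implementation phase do "trained CM providers in both conditions begin implementing the CM protocol with patients" (item 6.b).
- **Target population (items 2 and 3.c).** CM is to be offered to all patients admitted over 6 months.
- **Recruitment (items 2, 3.c and 4.c).** "Front-desk receptionist staff in each of the participating centers will give new patients that present to treatment a consent to contact form". Research staff then call interested patients, re-screen them and "obtain informed consent from up to 25 CM patients at each organization". Item 3.c also gives the center a role: "each center will be asked to enroll approximately one eligible CM patient per week to complete research assessment measures". Exclusions may be reported by center staff.
- **CM Exposure (item 9.a.i).** Sessions are extracted "for the 25 patients enrolled in the study", by center staff described as blind to condition.
- **CM Sustainment (item 9.a.iii).** The same extraction is applied to "25 randomly selected patients meeting eligibility criteria", who need not be research participants.
- **Bonus (item 7.b, E-ATTC only).** A provider earns $200 for every patient reaching 10 sessions. The same paragraph mentions 25 recruited patients and 2 to 5 providers per site. Item 9.a.i verifies the 10-session target by counting extraction forms.
- **Analysis (item 10).** Patient, staff and center covariates are tested as moderators or used as predictors. No comparison of enrolled with non-enrolled patients is planned.

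**The concern.** In a cluster trial, patients who enter after their cluster's allocation is known can differ between arms even when the clusters are well balanced. Two mechanisms matter here.

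1. **Differential recruitment.** If centers in one arm refer, or patients there agree, in a way related to how long patients stay or how often they attend, the counted groups differ in kind between arms. Item 4.c protects the balance of numbers between arms, not the type of patient.
2. **Concentration of sessions.** If E-ATTC providers are paid on counted patients and know who they are, they have an arm-specific reason to direct sessions to them. The count could then rise with little change for other admissions. Covariate adjustment cannot correct this.

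The trial asks whether centers make CM part of routine care for all new patients, and a gain confined to research participants would not show that. CM Exposure and CM Sustainment also rest on differently selected samples, so a change between phases mixes real change with a change in who is counted.

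**Working it through.** **Inputs.** 30 centers and 25 patients per center (items 2, 4.c, 9.a.i); average flow 17 new patients per month (4.c); minimum flow 5 per month (3.a); 6-month admission window (3.c); $200 per patient at target, $50 × 9 months = $450 for competence, 2 to 5 providers per site, mean salary $45,000, intended bonus about 6%, cited range 4–7% (7.b).

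**Step 1: the plan's own figures.** 30 × 25 = 750, as stated. 17 × 6 = 102, as stated. 25/102 = 24.5%, which the plan gives as 25%. Applying 25% exactly gives 0.25 × 102 × 30 = 765, within 2% of 750. The figures reproduce.

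**Step 2: coverage.** Expected admissions are 30 × 102 = 3,060. Not counted: 3,060 − 750 = 2,310, or 75.5%. At minimum flow, 5 × 6 = 30 admissions and 25/30 = 83% are counted. Coverage therefore varies widely by center.

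**Step 3: order of events.** Staff surveys at the start of Preparation are placed after randomization (8.b), and E-ATTC planning visits and calls run during Preparation (6.a). CM with patients starts about 5 months later. Eligible patients were admitted in the last 30 days (3.c). Counted patients are thus identified after their center's allocation. Blinding is stated for chart extraction and competence coding (9.a), not for referral, recruitment or consent.

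**Step 4: whom does the bonus cover?** Maximum per provider = (patients ÷ providers) × $200 + $450.

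| Patient base | Providers | Maximum | Share of $45,000 |
|---|---|---|---|
| 25 enrolled | 5 | 5 × 200 + 450 = $1,450 | 3.2% |
| 25 enrolled | 2 | 12.5 × 200 + 450 = $2,950 | 6.6% |
| 102 admissions | 5 | 20.4 × 200 + 450 = $4,530 | 10.1% |
| 102 admissions | 2 | 51 × 200 + 450 = $10,650 | 23.7% |

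The plan's 10-patient example gives $2,000 + $450 = $2,450, or 5.4%. Only the enrolled-patient base roughly fits 4–7%. Together with the extraction-form rule, this points to the paid patients being the counted patients.

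**Step 5: possible size, under assumptions not in the documents.**

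*Selective enrollment.* Suppose enrollment takes the top share p of a normally distributed tendency to enroll, which has correlation r with later session count. The enrolled mean then shifts by r × φ(z)/p standard deviations, where z cuts off the upper share p. At p = 0.245, φ(z)/p = 1.283, so r = 0.1, 0.2 and 0.3 give 0.13, 0.26 and 0.38 SD. At p = 0.833, φ(z)/p = 0.300, giving 0.03, 0.06 and 0.09 SD. An equal shift in both arms cancels; only a difference between arms biases the comparison. For example, at average flow, r = 0.1 in one arm and 0.2 in the other gives 0.257 − 0.128 = 0.13 SD, in either direction.

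*Concentration.* If uncounted patients get a fraction s of the arm effect seen in counted patients, the center-wide effect is 0.245 + 0.755 × s of the measured effect: 24.5% at s = 0, 43% at s = 0.25, 62% at s = 0.5 and 100% at s = 1.

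The document gives no power calculation, SD or intraclass correlation, so no corrected power can be computed. A random 25 per center keeps the planned number at 750.

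**The case against.** The strongest defense is that recruitment is largely out of CM providers' hands. Forms go to every new patient from the front desk, research staff make contact, screen and obtain consent, and exclusions are minimal. The models include age, race, sex and problem severity. The bonus is part of the strategy under test, so sessions it induces are a real effect of E-ATTC. And leaving most admissions uncounted is sampling, not bias in itself.

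Much of this stands, and it rules out several stronger readings:

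- A reader might infer that recruiting staff know the condition. No section says so. Coaching and bonuses go to leaders and CM providers, and no front-desk payment is described. The supportable statement is that recruiters are not stated to be blind.
- A reader might take the term CM patients to mean that entry depends on receiving CM. Item 3.c has three eligibility criteria and that is not one; item 2 says standard care may or may not include CM.
- A reader might treat the payment link as settled. Item 7.b does not restrict the bonus to enrolled patients, and no section says providers are told who enrolled.
- A reader might call the Sustainment sample unbiased. Item 9.a.iii does not say who draws it or from what list.

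The defense does not close the gap. Re-screening confirms eligibility, not representativeness. Covariates handle measured differences only. Blind extraction protects the count, not the choice of patients. A genuine effect in paid patients is still not evidence of delivery to everyone admitted.

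**Conclusion.** The concern holds as a risk to one primary-hypothesis outcome. CM Exposure rests on a consent-based sample formed after center randomization, covering 24.5% of admissions at average flow and 83% at minimum flow. Recruiter blinding is unstated, and there is no check of enrolled against non-enrolled patients. That E-ATTC bonuses fall on the same patients is an inference from the bonus sizing, the extraction-form rule and the salary arithmetic; the plan should settle it.

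The 75.5% left uncounted must not be read as the size of a bias: it describes reach. Distortion of the arm comparison requires recruitment to differ by arm, or sessions to be concentrated on counted patients in one arm. The documents show that neither is prevented; they do not show that either occurs, and they give no basis for its size. The Step 5 figures are illustrations only.

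**What to change.** 1. Define CM Exposure on 25 randomly selected eligible patients per center admitted in the 6-month window, regardless of research consent, using the extraction protocol planned for CM Sustainment. Have research staff draw the sample from the admission list, and write that into the plan.
2. In this analysis, adjust only for covariates available in the chart or at center and staff level.
3. Keep the count in enrolled patients as a supporting analysis, and report session counts for enrolled versus non-enrolled patients by arm.
4. State which patients the P4P exposure bonus covers.

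**Cost.** Up to 25 more patient charts per center (at most 25 × 30 = 750), with one form per recorded session. All sites have already agreed to document CM sessions in the medical record (item 8.d). Approval is needed to read charts of non-consented patients from the Implementation phase; the documents do not say whether existing approval extends that far. Interview-based covariates will be missing for patients who did not enroll.
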